### 17.3. Exploratory Efficacy

Not applicable.

# 18. QUALITY OF LIFE ANALYSIS

Not applicable.

### 19. SAFETY OUTCOMES

All outputs for safety outcomes will be based on the Run-in period and SAF populations.

There will be no statistical comparisons between the treatment groups for safety data, unless otherwise specified with the relevant section.

#### 19.1. Adverse Events

Adverse Events (AEs) will be coded using Medical Dictionary for Regulatory Activities (MedDRA) central coding dictionary, Version 25.1 or latest. AEs are recorded in the 'Adverse Events' form of the eCRF.

Treatment emergent adverse events (TEAEs) are defined as AEs that started or worsened in severity on or after the date/time of first dose of study medication.

TEAEs that occurred or worsened on or after the date/time of the first administration of Humira in the Run-in period but before the date/time of the first administration of Humira/ Hulio in the Randomized Interchangeable Treatment Period will be summarized under Run-in period population.

TEAEs that occurred or worsened on or after the date/time of the first administration of Humira/ Hulio in the Randomized Interchangeable Treatment Period will be summarized under SAF population.

If TEAE end date is missing and started in Run-in period then it will be part of Run-in period.

See Appendix 3 for handling of partial dates for AEs. In the case where it is not possible to define an AE as treatment emergent or not, the AE will be classified by the worst case, i.e., treatment emergent.

Document: \\ieedc-vnasc01\Biosdata\Viatris\HULIO\HAB34991\Biostatistics\Documentation\SAP

Author: Version Number: 2.0

Version Date: 29Nov2023

Template No.: CS\_TP\_BS016 Revision 7 Reference: CS\_WI\_BS005

Effective Date: 01Nov2021

Page 34 of 48

An overall summary of number of patients within each of the categories described in the sub-section below, will be provided as specified in the templates.

Listings will include TEAEs and Non-TEAEs.

Adverse event of special interest (AESI) defined in the protocol will be summarized and listed. AEs which are classified as "Event qualify AESI" as per Adverse event CRF form will be used.

#### **19.1.1.** All TEAEs

Incidence of TEAEs will be presented by System Organ Class (SOC) and Preferred Term (PT) and broken down further by maximum severity and relationship to study medication.

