Sensitivity Analyses: The AUC τ , $_{26\text{-}28}$ and C_{max} , $_{26\text{-}28}$ will be analysed using analysis of covariance (ANCOVA) model on the log transformed scale. This model will include treatment and covariates. Log transformed AUC $_{\tau,\ 10\text{-}12}$ or $C_{max,\ 10\text{-}12}$ will be used as covariates.

The secondary PK endpoint $C_{min\ 26-28}$ will be analyzed in the same way as the primary endpoints. However, even the mean ratio and CIs will be calculated and presented. No formal conclusion is required to be within BE limits.

The secondary PK endpoint $T_{max\ 26-28}$ will be analyzed in a descriptive manner only.

All PK analysis will be performed on the PK population.

Efficacy Analysis:

All secondary efficacy endpoint analyses will be based on the PP population.

The difference in proportions will be calculated as the difference between the observed proportions in each treatment group. An asymptotic 2-sided 90% confidence interval for the difference of proportions will be obtained using the Wald method.

Safety Analyses:

Treatment-emergent AEs, serious AEs and Adverse event of special interest (AESI) will be descriptively summarized by system organ class, preferred term, and treatment group.

Overall, descriptive summaries will be produced as well as according to severity and relationship to the study treatment.

Local tolerance and antibodies to adalimumab will be descriptively summarized by treatment group.

The safety analyses will be performed on the Safety and Run-in Period populations.

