### 2.2.2. Secondary Endpoints

The secondary endpoints are:

- Other adalimumab PK parameters, including Tmax, 26-28 and Cmin, 26-28 during the intensive PK sampling interval between Weeks 26 and 28 and Ctrough obtained at the scheduled PK sample time points.
- Proportion of PASI 50, PASI 75, PASI 90 and PASI 100 responders at Week 28
- Proportion of sPGA success (clear or almost clear) at Week 28
- Safety measures characterized by type, incidence, severity, timing, seriousness and relatedness of treatmentemergent adverse events (TEAEs) including injection site reactions [ISRs], hypersensitivity reactions, heart failure, malignancies, serious infections including tuberculosis [TB], and laboratory test abnormalities
- Incidence of positive anti-drug antibody (ADA) and neutralizing antibody (NAb) response and ADA titers at Week 28

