### 7. GENERAL CONSIDERATIONS

### 7.1. Reference Start Date and Study Day

All summaries by period defined in the SAP refers to the analysis period. The analysis period consists of screening, Run-in Period, and Randomized Interchangeable Treatment Period (study diagram). Each period is defined as below:

Screening period is defined as study period from informed consent date prior to administration of Humira at Week 1.

Run-in Period is defined as study period on or after administration of Humira at Week 1 and before randomization at Week 12, or until last study participation date if patients withdrew/discontinued before Week 12.

Randomized Interchangeable Treatment Period is defined as study period from the randomization at Week 12 until Week 28 or until last study participation date if patients withdrew/discontinued. While presenting the data Week 28 (EOT) assessment will also be included.

Overall period is defined as study period consisting of above 3 periods and including follow up (Week 30/EOS). Study Day will be calculated from the reference start date and will be used to show start/stop day of assessments and events. It will appear in every listing where an assessment date or event date appears.

Reference start date is defined as the day of the first dose of study medication, i.e., Humira in the Run-in Period (Week 1/Visit 1) (Day 1 is the day of the first dose of study medication).

- If the date of the event is on or after the reference date, then:
- Study Day = (date of event reference date) + 1.
- If the date of the event is prior to the reference date, then:
- Study Day = (date of event reference date).

In the situation where the event date is partial or missing, Study Day, and any corresponding durations will appear

Document: \\ieedc-vnasc01\Biosdata\Viatris\HULIO\HAB34991\Biostatistics\Documentation\SAP

Author: Version Number: 2.0

Version Date: 29Nov2023

Template No.: CS\_TP\_BS016 Revision 7 Reference: CS\_WI\_BS005

Page 21 of 48

partial or missing in the listings.

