# 19.8. Other Safety Assessments

The following summaries will be provided:

- A by-patient listing of Chest X-Ray data as recorded in the 'Chest X-Ray' form of the eCRF.
- A by-patient listing of pregnancy test data at screening visit as collected in the 'Pregnancy' form of the eCRF.
- A by-patient listing of serology test data at screening visit as collected in the 'Laboratory Assessment: Serology (HBsAg, HBcAb, HCVAb, HIV)' form of the eCRF.
- A by-patient listing of IGRA or Purified Protein Derivative Test data at screening visit as collected in the 'Laboratory Assessment: IGRA or Purified Protein Derivative Test' form of the eCRF.
- A by-patient listing of Urine Drug Screen data at screening visit as collected in the 'Laboratory Assessment: Urine Drug Screen' form of the eCRF.
- A frequency table for the injection site reactions: pain, tenderness, erythema/redness, induration/swelling, and pruritus (itching) will be presented along with a by-patient listing as collected in the 'Injection Site Reaction -Investigator Assessment' form of the eCRF.
- A by-patient listing of the monitor for signs and symptoms of TB and other serious infections, for progression to

Document: \\ieedc-vnasc01\Biosdata\\Viatris\HULIO\HAB34991\Biostatistics\Documentation\SAP

Author: Version Number: 2.0

Version Date: 29Nov2023

Template No.: CS\_TP\_BS016 Revision 7 Reference: CS\_WI\_BS005

Page 38 of 48

NYHA Class III/IV Heart failure2, and examination for non-melanoma skin cancer will be presented as recorded in the 'Signs and Symptoms' form of the eCRF.

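### Timing is a named attribute of the secondary safety endpoint, but SAP 19.1 specifies no adverse event summary by switch segment or time since dose

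*SAP*

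**What the plan says.** Both the protocol synopsis and SAP 2.2.2 define the safety endpoint as "Safety measures characterized by type, incidence, severity, timing, seriousness and relatedness" of treatment-emergent adverse events (TEAEs), and both name injection site and hypersensitivity reactions.

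SAP 19.1 makes one division in time. Events before the first randomised dose go to the run-in summary. Those on or after the "first administration of Humira/ Hulio in the Randomized Interchangeable Treatment Period will be summarized under SAF population". No end date and no subdivision of that stretch is given. SAP 19.1.1 then tabulates incidence by system organ class and preferred term, "broken down further by maximum severity and relationship to study medication". Further summaries cover discontinuation, seriousness, death and events of special interest (AESIs). SAP 19.1 does not itself set the columns. These follow from the protocol synopsis, where events are "descriptively summarized by system organ class, preferred term, and treatment group", and from SAP Appendix 1, which shows Group 1 and Group 2.

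On timing, SAP 7.1 says of Study Day: "It will appear in every listing where an assessment date or event date appears". Day 1 is the first run-in dose. SAP 19.8 adds "A frequency table for the injection site reactions" without saying whether it is by visit. SAP Appendix 1 labels the randomised visits Switch 1 (Weeks 12 and 14), Switch 2 (Weeks 16 and 18) and Switch 3 (from Week 20), but no adverse event summary is said to use those labels. SAP 3.3 records no change from the protocol analysis.

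**The concern.** The trial compares three switches with none. If switching provoked reactions, one would expect onset to gather after particular switches. A single cumulative incidence per group from Week 12 onward cannot show such a pattern. Listings carry a day count, but it starts at the run-in rather than at a switch or the latest injection, and a listing does not compare groups. Followed as written, the SAP summarises every other attribute of its own safety endpoint for adverse events and leaves timing to case-by-case reading.

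The pool also has no stated end. SAP 7.1 closes the randomised period at Week 28, while SAP 3.1 offers Hulio at Weeks 28 and 30 to both groups. Read literally, an event after optional Hulio in a Group 1 patient counts in the continuous-Humira column.

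**Working it through.** **Attributes against summaries**

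| Endpoint attribute | Adverse event summary in the SAP |
|---|---|
| Type, incidence | 19.1.1, system organ class and preferred term |
| Severity | 19.1.1.1 |
| Relatedness | 19.1.1.2 |
| Seriousness | 19.1.3 |
| Timing | Run-in versus randomised only (19.1); Study Day in listings (7.1) |

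**Inputs from the documents.** 165 patients per arm (SAP 4). Eight planned randomised injections (SAP 16), which the visit list confirms: Weeks 12, 14, 16, 18, 20, 22, 24 and 26. Group 2 receives Hulio for 4 weeks, Humira for 4 and Hulio for 8 (SAP 3.1), so 6 of its 8 injections are Hulio and 2 are Humira. The documents give no reaction rates, so the rates below are assumptions.

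**Rate ratio, constant background over 16 weeks**
- Risk doubled in Weeks 12 to 16 only: (12×1 + 4×2)/16 = 20/16 = 1.25 pooled, against 2.0 in the window.
- Risk doubled for 2 weeks after each of three switches: (10×1 + 6×2)/16 = 22/16 = 1.38 pooled, against 2.0.

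**Patient incidence, which is what the SAP tabulates.** Let b be the background risk per 2-week interval, with an excess of 5 percentage points in the interval after a switch. Over 8 intervals, Group 1 has 1 − (1−b)^8. With one switch affected, Group 2 has 1 − (1−b)^7 × (1−b−0.05).

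| b | Affected interval | Pooled |
|---|---|---|
| 0% | 5% vs 0% | 5% vs 0% |
| 0.5% | 5.5% vs 0.5% (ratio 11) | 8.8% vs 3.9% (2.2) |
| 1% | 6% vs 1% (6.0) | 12.4% vs 7.7% (1.6) |
| 2% | 7% vs 2% (3.5) | 19.3% vs 14.9% (1.3) |
| 5% | 10% vs 5% (2.0) | 37.1% vs 33.7% (1.1) |

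At b = 1% with 165 per arm, that is about 9.9 against 1.7 patients in the interval, and 20.4 against 12.7 pooled.

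If all three switches are affected at b = 1%, Group 2 has 1 − 0.99^5 × 0.94^3 = 21.0% against 7.7%. The difference grows to 13.3 points from 5 in a single interval, while the ratio falls from 6.0 to 2.7.

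**Which windows recover the signal.** Under the three-switch doubling, a 4-week segment shows (2×2 + 2×1)/4 = 1.5. The 8-week third segment shows (2×2 + 6×1)/8 = 1.25, which is lower than the pooled 1.38. Only a count of onsets within 14 days of the switch dose returns 2.0.

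**The case against.** The strongest reply is that the SAP follows the protocol. The synopsis plans adverse event summaries by class, term and group, overall and by severity and relationship. The secondary objective is to evaluate safety in the switching and non-switching arms, and no safety comparisons are planned. On that view the arm-level picture is the declared question, and mixing Hulio and Humira in Group 2 is the intervention itself. This stands as far as it goes: attributing events to one product is not a stated objective. It does not explain why timing is named in the endpoint and then has no adverse event summary.

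A reader might infer that a post-switch cluster is diluted in every safety table. The documents do not support that. The output templates, which govern table content (SAP 9), are not available. The layout of the injection site reaction table is unstated. Laboratory results, part of the same endpoint, are tabulated by visit (SAP 19.3). Nor does timing go wholly unreported, since listings carry Study Day.

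Dilution is also not automatic. With no background there is none, and an excess recurring after all three switches enlarges the pooled difference.

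**Conclusion.** The point holds as a gap in specification: a named endpoint attribute has no adverse event summary by switch segment or time since dose. A cluster after one switch can be masked in pooled incidence. A doubling confined to Weeks 12 to 16 would appear as 1.25. A 6-fold excess in one interval (6% against 1%) would appear as 1.6-fold. These sizes rest on assumed rates, a constant background above zero and an excess confined to one switch. An excess after all three switches would be visible in the pooled difference, without its timing. No primary conclusion and no type I error rate is touched, and nothing here suggests that a safety problem exists. If the templates already contain an onset table, the SAP should say so, and the point is then met.

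**What to change.** Add to SAP 19.1 and 19.8 descriptive tables by group of the number and percentage of patients with any TEAE, injection site reaction, hypersensitivity reaction and AESI, by onset interval: Week 12 to <16, 16 to <20 and 20 to <28, with events from Week 28 onward shown separately. Use the same calendar windows for Group 1. The denominator is patients still being followed on treatment at the start of each window; for the last window, where randomised dosing has ended, it is patients still in follow-up.

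Add rows for onset within 14 days of the Week 12, 16 and 20 doses, because the 8-week third window alone would dilute a post-switch cluster. State in SAP 19.1 where the window for the Safety population tables ends.

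The cost is SAP wording and a few tables from dates already collected. The downside is small counts per window, so the tables should remain descriptive, with no tests.

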#### 19.1.1.1. SEVERITY

Severity is classed as mild (grade 1)/ moderate (grade 2)/ severe (grade 3)/ life-threatening (grade 4)/ fatal (grade 5) based on CTCAE criteria, version 5.0. TEAEs starting after the first dose of study medication with a missing severity will not be classified. If a patient reports a TEAE more than once within that SOC/ PT, the AE with the worst-case severity will be used in the corresponding severity summaries.

#### 19.1.1.2. RELATIONSHIP TO STUDY MEDICATION

Relationship, as indicated by the Investigator, is classed as unrelated/ not related, Unlikely, possible, probable, and definite (increasing severity of relationship). A "related" TEAE is defined as a TEAE with a relationship to study medication as possible, probable, or definite to study medication. TEAEs with a missing relationship to study medication will be regarded as possible related to study medication. If a patient reports the same AE more than once within that SOC/ PT, the AE with the worst-case relationship to study medication will be used in the corresponding relationship summaries.

### 19.1.2. TEAEs Leading to Discontinuation of Study Medication

TEAEs leading to permanent discontinuation of study medication are those events for which 'Action Taken with study treatment' is recorded as 'Drug withdrawal' on the 'Adverse Events' form of the eCRF.

For TEAEs leading to discontinuation of study medication, summaries of incidence rates (frequencies and percentages) by SOC and PT will be prepared.

### 19.1.3. Serious Adverse Events

Serious adverse events (SAEs) are those events recorded as "Serious" on the 'Adverse Events' form of the eCRF. A

Document: \\ieedc-vnasc01\Biosdata\Viatris\HULIO\HAB34991\Biostatistics\Documentation\SAP

Author: Version Number: 2.0

Version Date: 29Nov2023

Template No.: CS\_TP\_BS016 Revision 7 Reference: CS\_WI\_BS005

Effective Date: 01Nov2021

Page 35 of 48

summary of serious TEAEs by SOC and PT will be prepared.

#### 19.1.4. Adverse Events Leading to Death

TEAEs leading to Death are those events which are recorded as 'Fatal' for the outcome field on the 'Adverse Events' form of the eCRF. A summary of TEAEs leading to death by SOC and PT will be prepared.

#### 19.2. Deaths

If any patients die during the study as recorded on the 'Death Details' form of the eCRF, the information will be presented in a summary table and a data listing using Run-in period and SAF populations.

### 19.3. Laboratory Evaluations

Results from the central laboratory will be included in the reporting of this study for Hematology and Serum Chemistry. Results from the local/central laboratory will be reported for Urinalysis. A list of laboratory assessments to be included in the outputs is included in the protocol, Section 7.3.2 (Table 5: Laboratory Safety Tests).

Presentations will be based on SI Units.

Quantitative laboratory measurements reported as "< X", i.e., below the lower limit of quantification (BLQ), or "> X", i.e., above the upper limit of quantification (ULQ), will be converted to X for the purpose of quantitative summaries, but will be presented as recorded, i.e., as "< X" or "> X" in the listings.

Descriptive summaries of observed values and change from baseline will be presented for clinical laboratory evaluations (Serum chemistry and hematology) by actual treatment group. Assessments of laboratory variables according to clinical relevance will be tabulated by visit and actual treatment group for each clinical laboratory parameter in frequency tables. Additionally, for each laboratory parameter, shifts in value from baseline to all post-baseline visits will be presented by actual treatment group in shift tables.

The assessment of categorical urinalysis variables will be tabulated by visit for each urine parameter by actual treatment group in frequency tables. Additionally, for each of the urine parameters, shifts in assessments from Baseline to all Post-baseline visits will be presented for each treatment group in shift tables.

For the shift tables, the normal laboratory ranges will be used to evaluate whether a particular laboratory test value was normal, low, or high for each post-baseline visit relative to whether the baseline value was normal, low, or high.

The following summaries will be provided for laboratory data by the actual treatment group:

Actual and change from baseline by visit (for quantitative measurements – Hematology and Serum Chemistry)

Document: \\ieedc-vnasc01\Biosdata\Viatris\HULIO\HAB34991\Biostatistics\Documentation\SAP

Author: Version Number: 2.0

Version Date: 29Nov2023

Template No.: CS\_TP\_BS016 Revision 7 Reference: CS\_WI\_BS005

Effective Date: 01Nov2021

Page 36 of 48

- Summary of the number and percentage of patients by visit (for qualitative measurements Urinalysis)
- Incidence of abnormal values according to normal range criteria
- Shift from baseline according to normal range criteria (for quantitative measurements and categorical measurements)
- A by-patient listing of all laboratory data

### 19.3.1. Laboratory Reference Ranges and Markedly Abnormal Criteria

Quantitative laboratory measurements will be compared with the relevant laboratory reference ranges in SI units and categorized as:

- Low: Below the lower limit of the laboratory reference range.
- Normal: Within the laboratory reference range (upper and lower limit included).
- High: Above the upper limit of the laboratory reference range.

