- 8. Is positive for human immunodeficiency virus (HIV), hepatitis C virus antibody, or hepatitis B surface antigen (HbsAg) or is positive for hepatitis B core antibody at Screening
- 9. Has laboratory abnormalities, including but not limited to clinically significant hematological abnormalities, that, in the opinion of the PI or designee, could

	cause this study to be detrimental to the subject. The subjects should be excluded if they have the following laboratory abnormalities				
	a.	Hemoglobin <9 g/dL			
	b.	Platelet count <100 000/mm ³			
	c.	White blood cell count <3000 cells/mm ³			
	d.	Aspartate aminotransferase and/or alanine aminotransferase that is persistently $\geq 2.5 \times$ the upper limit of normal. (Persistently indicates elevated transaminases, at least on two separate occasions)			
	e.	Creatinine clearance <50 mL/min (Cockcroft-Gault formula)			
	I	re progressive or uncontrolled, clinically significant disease that in the of the PI or designee renders the subject unsuitable for the study			
	11. Has a history of malignancy within 5 years except for adequately treated cutaneous squamous or basal cell carcinoma, in situ cervical cancer, or in sit breast ductal carcinoma				
	12. Has an active neurological disease, such as multiple sclerosis, Guillain-Barré syndrome, optic neuritis, and transverse myelitis, or a history of neurologic symptoms suggestive of central nervous system demyelinating disease				
	13. Has moderate to severe heart failure (New York Heart Association [NYHA Class III/IV)				
	14. Has a history of hypersensitivity to the active substance or to ar excipients of Humira or Hulio				
	15. Is pregnant or nursing (lactating) woman				
	I	ence (as assessed by the PI or designee using good clinical judgment) l or drug abuse or dependency up to 5 years prior to Screening			
	I	to follow study instructions and comply with the protocol in the of the PI or designee.			
Planned Number of Subjects	evaluable participants) would provide 90% power to demonstrate that the 90% confidence intervals (CIs) for the MR are within 80.00% to 125.00% for both primary PK parameters.				
	This study is To account for into the study	or 10% run-in failures, approximately 370 subjects will be enrolled			
Statistical Methods	Analysis Set All Subject I this study.	: Enrolled population: All subjects who provide informed consent for			

Version 2.0

This information is confidential to Viatris.

Page 9 of 91

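### The laboratory shift and incidence tables use low/normal/high only, so same-direction worsening from an abnormal baseline shows as no shift; the markedly abnormal criteria announced in SAP 19.3.1 are not given

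*SAP*

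**What the plan says.** **Classification.** SAP 19.3.1 is headed "Laboratory Reference Ranges and Markedly Abnormal Criteria". Its text reads "Quantitative laboratory measurements will be compared with the relevant laboratory reference ranges in SI units and categorized as" Low, Normal or High. The top level is "High: Above the upper limit of the laboratory reference range", and Low is its mirror image. No markedly abnormal criterion or cross-reference follows, and nothing there looks redacted.

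**Tables built on it.** For the shift tables, SAP 19.3 says "the normal laboratory ranges will be used to evaluate whether a particular laboratory test value was normal, low, or high" at each post-baseline visit "relative to whether the baseline value was normal, low, or high". The incidence of abnormal values also uses the normal range.

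**Baseline.** Under SAP 7.2, the hematology and chemistry baseline for the randomised period is the last value before the first dose of that period (Week 12). No range requirement is attached.

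**Eligibility.** Exclusion 9 in the protocol synopsis lists:
- "Hemoglobin <9 g/dL"
- platelets below 100 000/mm³
- white cells below 3000/mm³
- "Aspartate aminotransferase and/or alanine aminotransferase that is persistently" at or above 2.5 x ULN, where persistence means at least two occasions
- creatinine clearance below 50 mL/min

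It also has a general clause for any laboratory abnormality that the investigator considers could make participation detrimental.

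**Other laboratory outputs.** SAP 19.3 plans frequency tables by clinical relevance, summaries of observed values and change from baseline, and a listing of all values. Adverse event severity is graded "based on CTCAE criteria, version 5.0" (SAP 19.1.1.1).

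**The concern.** A three-level shift table registers only movement across a reference limit. A patient who starts outside the range and moves further in the same direction stays in the same cell. The eligibility limits leave room for such patients at entry. The Week 12 reset adds those whose values left the range during the Humira run-in, which matters because the comparison of switching with continued Humira starts there.

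The incidence table has the companion problem: a value just over the limit and a very high one each count as one abnormality.

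Laboratory abnormalities belong to the secondary safety endpoint on treatment-emergent adverse events, which is characterised by severity among other attributes (SAP 2.2.2). SAP 19 plans no between-group safety tests unless otherwise specified, so a reader comparing laboratory safety between arms depends on the descriptive tables.

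**Working it through.** The plan gives no figure to reproduce. The check applies the SAP's own rule to baselines that the listed eligibility limits permit.

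**Rule (SAP 19.3, 19.3.1).** Category(x) = Low if x < LLN, High if x > ULN, otherwise Normal. A shift is seen only if Category(post-baseline) differs from Category(baseline).

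**AST/ALT, in multiples of ULN.** No laboratory-specific range is needed. Baselines of 1.01 to 2.49 fall below the 2.5 x ULN limit in exclusion 9. The post-baseline values of 3, 5, 10 and 20 are illustrations. Entries are fold rise = post-baseline / baseline.

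| Baseline | to 3 | to 5 | to 10 | to 20 |
|---|---|---|---|---|
| 1.01 | 2.97 | 4.95 | 9.90 | 19.80 |
| 1.50 | 2.00 | 3.33 | 6.67 | 13.33 |
| 2.00 | 1.50 | 2.50 | 5.00 | 10.00 |
| 2.49 | 1.20 | 2.01 | 4.02 | 8.03 |

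All 16 cells are High to High, so the shift table shows no change in 16 of 16. For the randomised period even 2.49 is not an upper bound, because SAP 7.2 sets no limit at Week 12.

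**Low direction.** The documents give no lower reference limits, so these are assumed.
- Platelets 100 to 20 x10⁹/L: Low to Low for assumed lower limits of 130, 140 and 150.
- Hemoglobin 9.0 to 6.5 g/dL: Low to Low for assumed lower limits of 11.5, 12 and 13.

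Both starting values sit on the permitted side of exclusion 9.

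**Would the mean change show it?** One patient going from 2.49 to 10 x ULN changes by 10 - 2.49 = 7.51. With 165 patients per arm (SAP 4), the arm mean moves by 7.51/165 = 0.046, about 0.05 x ULN. The minimum and maximum (SAP 8) would show that an extreme value exists.

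**What each planned output provides:**

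| Output | Patients counted per arm | Against baseline | By size |
|---|---|---|---|
| Shift table | yes | yes | no |
| Incidence table | yes | no | no |
| Clinical-relevance table | yes, by visit | no | categories undefined |
| Change-from-baseline summary | no | yes | through min/max only |
| Listing | no | readable by hand | readable by hand |
| Graded adverse events | yes | not stated | yes, if reported as an adverse event |

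No row combines all three.

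**The case against.** The strongest reply is that the worsening is absent from certain tables, not from the report. An extreme change appears in the minimum or maximum, every value is listed, and clinical relevance is a second classification. An abnormality reported as an adverse event is graded by CTCAE and tabulated by maximum severity (SAP 19.1.1). This stands. A reader might infer from 19.3.1 that low/normal/high is the only classification anywhere, or that severe worsening would go unseen; the documents support neither. What remains is that no output counts patients per arm by size of worsening, clinical relevance is undefined, and adverse event grading depends on reporting.

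A reader might also infer that exclusion 9 screens out only a few named tests. It does not: it has the general investigator clause and a creatinine clearance limit, and exclusions 5 and 10 add further judgement. Out-of-range entry remains possible but is narrower than the numerical limits alone suggest.

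Third, laboratory abnormality might be read as a secondary endpoint of its own. The wording is more naturally read as part of the adverse event endpoint, for which grading is already planned. The laboratory tables are then supporting evidence.

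Finally, the output templates (SAP 9) and the full protocol's laboratory section are not available here and may define marked or clinically relevant categories. If so, 19.3.1 should cite them; as written it does not.

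**Conclusion.** The point holds for the shift and incidence tables. Under the SAP's own rule, same-direction worsening from an out-of-range baseline is tabulated as no shift, whatever its size, and the criteria promised in the 19.3.1 heading are missing. For AST/ALT this follows from the documents alone. For hemoglobin and platelets it rests on the assumed reference limits shown.

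How many patients this touches is unknown: the documents do not give the share out of range at entry or at Week 12, and no figure should be attached. The consequence is limited to descriptive safety reporting. The PK equivalence conclusion does not depend on it. The change is worth making because it is cheap and uses data already collected.

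**What to change.** In SAP 19.3.1:

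1. Supply the severity categories that the heading announces: either CTCAE v5.0 grades, already adopted for adverse events in 19.1.1.1, or stated markedly abnormal thresholds. Keep low/normal/high for tests without a grade.
2. Tabulate baseline category by worst post-baseline category, by treatment group, separately for the run-in (a single Humira column) and the randomised period, using the baselines in SAP 7.2. State whether unscheduled results count towards the worst value, since SAP 7.3 leaves them out of by-visit summaries.
3. Count the patients with any increase in category, by group.
4. Define the clinical-relevance categories in 19.3 and say who assigns them.

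If the templates already contain such categories, a cross-reference would cover step 1. The cost is SAP wording, one derivation and one set of tables. No new data are needed; the downside is a little more programming.
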